	Discharge rating scale scores more than 9 points, patients can be accompanied by relatives and friends. The incidence of hypoxia ($75\% \leq \text{SpO}_2 < 90\%$, $\leq 60\text{s}$) and severe hypoxia ($\text{SpO}_2 < 75\%$ or $75\% \leq \text{SpO}_2 < 90\%$, $\geq 60\text{s}$) during anesthesia were recorded. The incidence of choking, reflux aspiration and laryngeal spasm were recorded. The time of intervention was half or disappearance of end-expiratory carbon dioxide and/or disappearance of thoracic fluctuation and/or $\text{SpO}_2 < 95\%$, that is, open airway manipulation was taken successively until $\text{SpO}_2 \geq 95\%$, and the last means of opening the airway was recorded. The means of opening the airway of the two groups were the same, including: 1) adjusting the oxygen flow; 2) Lift the lower jaw; 3) Mask ventilation (pull out the gastroscope if necessary); 4) Tracheal intubation or laryngeal mask for ventilator assisted ventilation.
Shedding/culling criteria	After postoperative recovery, patients were assessed for adverse reactions. The score of discharge scale after sedation/anesthesia was more than 9 points. Patients could be accompanied by relatives and friends to leave the hospital.
Shedding/culling criteria	Patients who were lost to follow-up, had adverse events, or voluntarily withdrew from the trial
Early exit criteria	Patients with severe airway spasm, obstruction of ventilation, inability to effectively improve airway, and need emergency tracheal intubation or cricothyroid puncture.
Primary outcome measure	Incidence of hypoxia ($75\% \leq \text{SpO}_2 < 90\%$, $\leq 60\text{s}$) during anesthesia and sedation.
Secondary outcome measure	1, severe hypoxia ($\text{SpO}_2 < 75\%$ or $75\% \leq \text{SpO}_2 < 90\%$, $\geq 60\text{s}$) 2, the incidence of airway intervention 3, intraoperative dose of additional drugs 4, endoscopist satisfaction 5, recorded adverse events: choking, laryngeal spasm and reflux aspiration incidence; Apnea or slow breathing episodes (defined as respiratory rate ≤ 6 beats/min); Bradycardia is defined as a heart rate ≤ 50 beats/min. Serious adverse events such as tracheal intubation, non-invasive ventilation, use of vasopressors, and hospitalization are required.

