Safety index	1. Primary outcome measures: incidence of hypoxia 2. Secondary outcome measures: (1) incidence of airway intervention (2) monitoring of vital signs at different time points 3. Adverse events: (1) Intraoperative laryngeal spasm, reflux aspiration, hypotension, hypoxia saturation, respiratory depression, bradycardia/tachycardia etc. (2) postoperative: Pharyngeal pain, oropharyngeal hemorrhage, wake score, etc. 4. Satisfaction: patient, endoscopist
Statistical analysis method	SPSS22.0 statistical software package was used for statistical analysis, and the measurement data were expressed in the form of mean \pm standard deviation ($x \pm S$). Independent sample t test was used for statistical analysis of the data with normal distribution or transformed data conforming to normal distribution. For non-normal data, wilcoxon rank sum test was used to compare inter-group analyses. Counting data were represented by frequency (%), and Chi-square test was used for statistical analysis. $P < 0.05$ was considered to be statistically significant.
Research progress plan	1. From July 2024 to August 2024, improve the study design, formulate relevant CRF tables, pass ethics and register online; 2. From August 2024 to May 2025, complete case enrollment; 3. From June 2025 to September 2024, summarize data, make statistical analysis, and write the paper
Form of publication of research results	The results of the study will be published in the form of a paper, and 1-2 articles included in SCI will be published.

一、 Objective

1. Primary outcome measures

To investigate the incidence of novel oropharyngeal airway hypoxia ($75\% \leq \text{SpO}_2 < 90\%$, $\leq 60\text{s}$) during anesthesia in patients with obstructive sleep apnea hypopnea syndrome undergoing painless gastroenteroscopy.

2. Secondary outcome measure

(1) Incidence of severe hypoxia ($\text{SpO}_2 < 75\%$ or $75\% \leq \text{SpO}_2 < 90\%$, $\geq 60\text{s}$)

(2) The incidence of airway intervention required

(3) the dosage of additional drugs during the operation was recorded

(4) the satisfaction of endoscopists was recorded

(5) Adverse events were recorded: the incidence of choking, laryngeal spasm and reflux aspiration were observed; Apnea or slow breathing episodes (defined as respiratory rate ≤ 6 beats/min); Bradycardia is defined as a heart rate ≤ 50 beats/min. Serious adverse events such as tracheal intubation, non-invasive ventilation, use of vasopressors, and hospitalization are required.

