
must be avoided and conscious intubation under surface anesthesia or guided intubation under fiberoptic bronchoscope should be adopted [4]. To sum up, airway management in obese patients is a clinical focus and difficulty. In order to reduce the trauma of patients and promote ERAS, endotracheal intubation is often not possible during the operation of painless gastroenteroscopy. Therefore, it is a topic worthy of our exploration to not only meet the comfort requirements of patients, but also ensure the safety of patients during the whole perioperative period. Whether the birth of new oropharyngeal airway can solve the ventilation problem of obese patients during anesthesia is the significance of this research.

【reference】

- [1] Zeng Shiying, ZHANG Longyu, ZHAO Xinyuan, ZHANG Jin, BAI Junyun. Effect of nasal continuous positive airway pressure on patients with obstructive sleep apnea syndrome [J]. World Journal of Sleep Medicine, 2021, 8(03):537-538.
- [2] Pang Congyi, Yi Jingde. Effect of nasal continuous positive airway pressure on patients with chronic heart failure complicated with obstructive sleep apnea hypopnea syndrome [J]. Medical food therapy and health, 2021, 19(12):48-49.
- [3] Liu Xiaojie, Li Dajiang, Ning Jishun, et al. A case of severe hypoxemia in obese patients undergoing radical general anesthesia for colon cancer [J]. Journal of Clinical Anesthesiology, 2016, 32(05):518.
- [4] Hang Yannan. Handbook of Contemporary Anesthesia [M]. 2nd Ed. Beijing: World Book Publishing House, 2011: 358-363.

Research content:

1. Study population

The principal investigator was responsible for recruitment under strict control, and 130 patients with obstructive sleep apnea hypopnea syndrome (diagnosed as OSAHS by polysomnography monitoring) who underwent painless gastrocolonoscopy from today were selected. They were informed and consented to this clinical trial.

2. Sample size calculation:

According to the pre-test results, the incidence of hypoxia in the test group and the control group were 0.2 and 0.5, respectively. The sample size was calculated using PASS software, and the bilateral test level $\alpha=0.05$ and the test efficacy power=0.9

were set. 52 cases were required in each group according to the incidence of hypoxia, and 65 cases in each group were calculated after considering 20% shedding rate, totaling 130 cases.

3. Specific research content:

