(1) The statistical analysis plan will be developed before the end of the trial and determined before the database is locked. Including statistical description and analysis methods, all statistical tests were carried out by bilateral test and SPSS22 was used for

statistics. For patient information, if it is a continuous variable and follows normal distribution, it is described by mean \pm standard deviation, and the difference between groups is compared by T-test. Those who did not follow the normal distribution were expressed as the median (upper and lower quartile), and the difference between groups was compared using the non-parametric rank sum test (Mann-WhitneyU test). For categorical variables such as the incidence of hypoxia, the frequency and rate (or composition ratio) were expressed, and the difference between groups was compared by Chi-square test or Fisher exact probability method.

(2) Main indicators:

- 1) Intraoperative hypoxia was described by frequency (incidence) and Chi-square test or Fisher analysis was intended to determine whether there was a difference in the incidence of hypoxia between the two groups. Test $P < 0.05$ was considered statistically significant, and confidence interval was 95%.
- 2) Processing of missing data: Missing data or illogical data delete cases with missing values or use missing value filling methods (mean interpolation, maximum likelihood estimation, or multiple interpolation, etc.).
- 3) It is planned to collect clinical data and CRF tables of all subjects for examination, data entry and statistical analysis before May 2025.

Description of the new oropharyngeal airway used in the test

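### The primary outcome counts only brief, moderate desaturation, so a patient whose only episode lasts longer than 60 s is scored as having no primary event

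*Protocol*

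**What the plan says.** The scheme summary of the Protocol gives the primary outcome as "Incidence of hypoxia ($75\% \leq \text{SpO}_2 < 90\%$, $\leq 60\text{s}$) during anesthesia and sedation". The Objective section repeats the same limits: "To investigate the incidence of novel oropharyngeal airway hypoxia ($75\% \leq \text{SpO}_2 < 90\%$, $\leq 60\text{s}$) during anesthesia". The event is therefore bounded in depth (not below 75%) and in duration (not above 60 s).

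Deeper or longer desaturation is a separate class, listed first among the secondary outcomes: "Incidence of severe hypoxia ($\text{SpO}_2 < 75\%$ or $75\% \leq \text{SpO}_2 < 90\%$, $\geq 60\text{s". Section 3, Specific research content, records the two classes separately in the same way.

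In the Statistical analysis plan section of the Protocol, under Main indicators, the primary comparison reads: "Intraoperative hypoxia was described by frequency (incidence) and Chi-square test or Fisher analysis". It has no rule that severe episodes also count, no composite, and no rule for a patient with several episodes.

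The sample size section takes pre-test results in which "the incidence of hypoxia in the test group and the control group were 0.2 and 0.5, respectively", with "the bilateral test level $\alpha=0.05$ and the test efficacy power=0.9". It does not say whether those rates include severe hypoxia.

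**The concern.** The study asks whether the device lowers the incidence of hypoxia in patients whom the protocol itself describes as being at raised respiratory risk. The event that carries the sample size and the primary test leaves out the worse part of that outcome. A patient whose only desaturation is prolonged is pooled with patients who never desaturated.

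The primary result can then move the wrong way:

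- If an intervention lets brief episodes run past 60 s, primary events disappear and it appears beneficial.
- If it shortens long episodes to under 60 s, primary events are created and it appears harmful.
- If it abolishes long episodes altogether, it earns no credit in the primary test.

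The trial is open (Research Methods, item 3). Staff who know the allocation can influence how long an episode lasts, and duration decides on which side of the definition a patient falls. The primary and safety results could contradict each other, with no rule for which to believe.

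A smaller defect is that an episode of exactly 60 s at 75–90% meets both definitions.

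**Working it through.** **1. The plan's own figure.** Inputs from the sample size section: p_T = 0.2, p_C = 0.5, two-sided α = 0.05, power 0.9, 20% dropout. With pooled variance, no continuity correction and mean rate p̄ = 0.35:

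n = [1.960·√(2·0.35·0.65) + 1.282·√(0.2·0.8 + 0.5·0.5)]² / 0.30² = (1.322 + 0.821)² / 0.09 ≈ 51.01, rounded up to 52 per group.

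52 / 0.8 = 65 per group, 130 in total. The stated 52, 65 and 130 reproduce exactly. The problem is the outcome definition, not the arithmetic.

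**2. How single-episode patients are scored.**

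| Only episode | Primary | Severe (secondary) |
|---|---|---|
| None | no | no |
| 85% for 30 s | yes | no |
| 80% for 60 s exactly | yes | yes |
| 80% for 3 min | **no** | yes |
| Below 75% | no, unless the passage through 75–90% is counted | yes |

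The fourth row is the defect. It holds whichever way the fifth row is read.

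**3. Power if 0.2 and 0.5 mean any saturation below 90%.** This is an assumption, and so are the severe-only shares, because the protocol gives neither. Scored rate = any-hypoxia rate × (1 − severe-only share). Power is exact, by enumerating the uncorrected two-sided chi-square test at 52 per arm.

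| Severe-only share, control / test | Scored rate, control / test | Power |
|---|---|---|
| 0 / 0 | 0.50 / 0.20 | 0.910 |
| 5% / 5% | 0.475 / 0.19 | 0.886 |
| 10% / 10% | 0.45 / 0.18 | 0.860 |
| 20% / 20% | 0.40 / 0.16 | 0.799 |
| 30% / 0% | 0.35 / 0.20 | 0.411 |

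By the formula in step 1, equal shares of 10%, 20%, 30% and 40% would need 61, 72, 87 and 106 per group for 90% power. At 60% in control and 0% in test, both scored rates are 0.20 and a real difference in any hypoxia vanishes from the primary.

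**4. Wrong direction.** Suppose any hypoxia is equal at 0.50 in both arms, with severe-only shares of 50% in test and 10% in control. Scored rates are 0.50 × 0.5 = 0.25 (test) and 0.50 × 0.9 = 0.45 (control). The probability of a significant result is 0.585 at 52 per arm and 0.683 at 65 per arm, practically all of it in favour of the device, although that arm has more severe hypoxia.

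The same in counts, with 26 of 52 patients below 90% in each arm:

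- Severe-only in 2 controls and 16 test patients: scored events are 24/52 against 10/52, chi-square 8.56, p = 0.003, favouring the arm with more severe hypoxia.
- Severe-only in 16 controls and 6 test patients: scored events are 10/52 against 20/52, chi-square 4.68, p = 0.03, against the arm with less severe hypoxia.

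**5. If 0.2 and 0.5 already describe the narrow band.** Then the present definition costs no power. Widening to any saturation below 90% adds the severe-only patients. Power at 52 per arm (normal approximation, which gives 0.906 for the plan as written) is:

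| Added, control / test | Any below 90%, control / test | Power | n per group for 90% |
|---|---|---|---|
| 5% / 0% | 0.55 / 0.20 | 0.968 | 39 |
| 10% / 5% | 0.60 / 0.25 | 0.961 | 40 |
| 10% / 10% | 0.60 / 0.30 | 0.879 | 56 |

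In these cases 52 per group stays about adequate after the change.

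**The case against.** **The reading is literal.** The protocol never says in words that a severe case is a primary non-event. The overall aim, the safety index, the sample size and the analysis section all speak of hypoxia without limits. That is so, but where the outcome is defined, in the summary and again in the objective, the limits are explicit. An unqualified word elsewhere does not override them. Nor is this a detail left for a later analysis plan, because the duration cap is part of the primary outcome itself.

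**Not every severe case is lost.** A patient with a long episode and a separate brief one still counts, and a fall below 75% passes through the 75–90% band. Both points stand. They limit the certain loss to patients whose only episode is prolonged.

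**Severe hypoxia is still reported.** As a secondary outcome it is compared too, so a shift from mild to severe would be visible. This is correct, but the one powered comparison could still point the other way.

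**The frequency is unknown.** Airway manoeuvres start at a saturation threshold above 90%, so prolonged-only cases may be uncommon. (The protocol gives this threshold as both 92% and 95%; those passages need reconciling in their own right.) With a 5% severe-only share in each arm, power is 0.886 against 0.910, a small loss, and the false-benefit case is extreme. This limits the likely size but does not justify the definition.

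**The overlap at 60 s is minor.** Agreed. It touches only episodes recorded at exactly 60 s.

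**Conclusion.** The concern holds and must be fixed. As defined, the primary outcome scores a patient whose only desaturation is prolonged the same as one with no desaturation, and the primary comparison can move against the true direction of benefit.

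The size cannot be fixed from the document, which gives no severe-hypoxia rate and does not say what 0.2 and 0.5 measure. If they are rates of any saturation below 90%, exact power at 52 per arm ranges from 0.886 (5% severe-only in each arm) through 0.799 (20% in each) to 0.411 (30% of control, none of test). If they are rates of the narrow band, no power is lost now, but the outcome still does not measure what the trial sets out to show. The false-benefit probability of 0.59 to 0.68 illustrates the direction of the error and is not a forecast.

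**What to change.** - Define the primary event per patient as any saturation below 90% during anesthesia and sedation, whatever its depth or duration: hypoxia or severe hypoxia as the protocol now labels them. A per-patient definition also settles how several episodes are handled.
- Keep severe hypoxia as a secondary outcome. Report each arm in three levels: none, hypoxia only, severe, with each patient classed by the worst episode.
- Make the duration classes disjoint: under 60 s against 60 s or more.
- State whether the pre-test rates of 0.2 and 0.5 refer to this definition. If they do not, restate the power with rates that do.

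Both classes are already recorded, so no new data are needed, and no extra patients unless the restated power calls for them. The change redefines the primary endpoint of an open trial, so it needs a protocol amendment with ethics committee approval, and should be made before any outcome data are compared by arm. The one loss is that the primary no longer isolates mild hypoxia, which the three-level table still shows.

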Research program	
Heart rate, pulse oxygen saturation (SpO₂), end-expiratory carbon dioxide, ECG monitoring, and noninvasive blood pressure (measured every 3 minutes) were routinely monitored before anesthesia induction. In this study, SAS was used to achieve simple randomization: 1. In the group using the new oropharyngeal airway (test group), oxygen was continuously supplied through a catheter connected to the endoscopic bites until the end of the gastroenteroscopy before induction of anesthesia. 2. In the conventional endoscopic bite group (control group), oxygen was continuously supplied through a conventional nasal catheter before induction of anesthesia and until the end of gastroenteroscopy. Before anesthesia induction, patients in the experimental group received 5-6L/min of oxygen for about 1min through the endoscopic bite connecting oxygen supply device, and patients in the control group inhaled 5-6L/min of oxygen for about 1min through the nasal catheter. Propofol 3mg/kg and sufentanil 7μg were used to induce anesthesia in both groups. Sufentanil was given at the beginning of pre-oxygen inhalation, and propofol was given 1min later. When participants achieved sufficient sedation (about BIS40), the new oropharyngeal airway group was placed into the oropharyngeal airway through the endoscopic bite and then began gastroscopy. The ordinary endoscopic bite group began to perform endoscopic operation after sufficient sedation was achieved. In both groups, 5mg/kg·h propofol was injected continuously to maintain anesthesia until the examination was completed. If participants showed frowning or slight body movement during diagnosis and treatment, 40 to 50mg of propofol was added intravenously. If HR < 50 times/intravenous injection of atropine 0.5mg; MAP < 60mmHg intravenous hydroxyamine 1mg; When SpO₂ < 92%, artificial airway intervention such as jaw support, assisted breathing or mask was given. After the examination is completed, the patient should not leave the examination room until the MOAA/S is 3-4 points. If the sedation/anaesthesia

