Study participants entered the examination room to establish intravenous access, using 2% lidocaine gel 5ml containing mouth cavity and pharynx. Heart rate (HR), pulse oxygen saturation (SpO₂), end-expiratory carbon dioxide, IPI (composite lung index), ECG monitoring, and non-invasive blood pressure (measured every 2.5 minutes) were routinely monitored before anesthesia induction. Ask patient to lie on left side.

In this study, the investigators planned to implement simple randomization using SAS:

(1) The group using the new oropharyngeal airway (test group) : Oxygen was continuously supplied through a catheter partially attached to the endoscopic mouth before induction of anesthesia until the end of gastroenteroscopy.

(2) In the conventional endoscopic bite group (control group), oxygen was continuously supplied through a common nasal catheter before induction of anesthesia until the end of gastroenteroscopy.

The entire trial operation process was completed by the investigators participating in the clinical trial. Before induction of anesthesia, study participants in the experimental group received 5-6L/min of oxygen for about 1 minute through an endoscopic biting oxygen supply device, and participants in the control group inhaled 5-6L/min of oxygen for about 1 minute through a nasal catheter. Propofol 3mg/kg and sufentanil 7 μ g were used to induce anesthesia in both groups. Sufentanil was given at the beginning of pre-oxygen inhalation, and propofol was given 1min later. When participants achieved sufficient sedation (about BIS40), the new oropharyngeal airway group was placed into the oropharyngeal airway through the endoscopic bite and then began gastroscopy. The ordinary endoscopic bite group began to perform endoscopic operation after sufficient sedation was achieved. In both groups, 5mg/kg·h propofol was injected continuously to maintain anesthesia until the examination was completed. If participants showed frowning or slight body movement during diagnosis and treatment, 40 to 50mg of propofol was added intravenously. If HR < 50 times/intravenous injection of atropine 0.5mg; MAP < 60mmHg intravenous hydroxyamine 1mg; When SpO₂ < 92%, artificial airway intervention such as jaw support, assisted breathing or mask was given. After the examination, study participants were not allowed to leave the examination room until they had a

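### Serial vital signs: the only stated tests for continuous data ignore the pre-induction readings, which costs precision and, if each time point is tested separately, raises the false-positive risk

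*Protocol*

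**What the plan says.** The Safety index in the Scheme summary includes, among its secondary measures, "monitoring of vital signs at different time points". It does not say how many time points there are or when they fall.

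The same signs are observed before induction. The Scheme summary (Research program) has "noninvasive blood pressure (measured every 3 minutes) were routinely monitored before anesthesia induction", with heart rate in the same list. Research content, section 3, has "non-invasive blood pressure (measured every 2.5 minutes) were routinely monitored before anesthesia induction", again with heart rate. The two passages give different blood pressure intervals and need to be reconciled.

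The analysis of continuous data is described twice. The Scheme summary (Statistical analysis method) states "Independent sample t test was used for statistical analysis of the data with normal distribution or transformed data conforming to normal distribution" and "For non-normal data, wilcoxon rank sum test was used to compare inter-group analyses". The Statistical analysis plan section of the protocol, under 2(1), says of normally distributed continuous variables that "the difference between groups is compared by T-test", with the Mann-Whitney test otherwise. Tests are two-sided and judged at 0.05. Neither place mentions a covariate, a change from baseline, a repeated-measures model or a multiplicity rule.

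**The concern.** Resting heart rate and blood pressure differ between patients, and those differences largely persist into the procedure. A two-sample test on the intraoperative value leaves that predictable variation in the error term, although the reading that would remove it has already been taken. A real haemodynamic difference between the airway devices is then harder to detect.

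The readings are also repeated within patients. The stated tests compare two groups on one value per patient. An analyst who follows the text literally would either pick one time point or run the same test at each of them. The second course gives several chances at P < 0.05 for one vital sign, with nothing in the protocol to hold the overall error at 5%.

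Safety of the device is one of the study's stated aims, so both a missed difference and a spurious one would matter to how the safety results are read.

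**Working it through.** **The protocol's own figure.** The sample size rests on the binary hypoxia outcome: rates 0.2 and 0.5, two-sided alpha 0.05, power 0.90. With pooled variance and no continuity correction, n = [1.960·√(2·0.35·0.65) + 1.282·√(0.2·0.8 + 0.5·0.5)]² / 0.3² = (1.322 + 0.821)² / 0.09 ≈ 51.0, rounded up to 52 per group. Then 52/0.8 = 65 per group, 130 in total. The stated 52, 65 and 130 are reproduced. No figure is given for the vital signs.

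**Inputs.** From the protocol: 52 evaluable or 65 enrolled per group, and two-sided 0.05 per test. Assumed, because the protocol gives none of them: a true difference of 0.5 SD, a correlation ρ of 0.3, 0.5 or 0.7 between baseline and later value, 4 to 8 time points, and a within-patient correlation of 0.5 to 0.9 between time points.

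**Precision.** Adjusting for baseline multiplies the error variance by 1 − ρ², that is 0.91, 0.75 or 0.51. The standardized difference becomes d/√(1 − ρ²), so 0.5 becomes 0.524, 0.577 or 0.700. The noncentrality parameter is this value times √(n/2). Power from the noncentral t distribution:

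| n per group | Unadjusted | ρ = 0.3 | ρ = 0.5 | ρ = 0.7 |
|---|---|---|---|---|
| 52 | 71% | 75% | 83% | 94% |
| 65 | 81% | 84% | 90% | 98% |

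The gain is about 4, 12 and 23 points at 52 per group, and about 3.5, 10 and 17 points at 65. At ρ = 0.3 it stays below 5 points at either size.

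**Validity of one test.** With no true difference, a single unadjusted t test rejected in 4.9% of 20,000 simulated trials. Its error rate is as nominal.

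**Repeated testing.** If the k tests were independent, the chance of at least one P < 0.05 would be 1 − 0.95^k: 18.5% for k = 4 and 33.7% for k = 8. Readings on the same patient are correlated, which lowers this. Simulation under no difference (52 per group, equal correlation between time points, 20,000 trials per setting) gave, for one vital sign:

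| Correlation | 4 time points | 8 time points |
|---|---|---|
| 0.5 | about 15% | about 25% |
| 0.7 | about 14% | about 20% |
| 0.9 | 9–10% | about 12% |

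The range is thus roughly 9% to 25%. Several vital signs together would raise it further.

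**The case against.** The strongest reply is that the protocol never says vital signs are t-tested at each time point. The t test is a general rule for measurement data. Section 2(1) introduces it for patient information, and it has natural uses with no baseline, such as additional drug dose and satisfaction scores. A detailed analysis plan is still to be written before database lock, and a covariate or repeated-measures model for a safety variable often belongs there. Vital signs appear only under the Safety index, not in either list of secondary outcomes, and hypotension and bradycardia/tachycardia are separately recorded as adverse events.

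Most of this stands and limits the point. It does not remove it, because the protocol does not leave the method open. It states the between-group methods for continuous data in two places, all of them unadjusted, and offers nothing else for serial readings. A later plan that follows this wording would inherit the weakness.

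A reader might infer three stronger things that the documents do not support:

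- **That the unadjusted comparison is biased**, because simple randomization can leave the groups unequal at baseline. Chance imbalance is already allowed for in the test's 5% error rate. What is lost is precision.
- **That the plan commits itself to a separate test at every time point.** That is an inference from the absence of any other tool, and the number of time points is not fixed.
- **That the trial's main conclusion is at risk.** The hypoxia comparison and its sample size do not depend on vital-sign means.

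**Conclusion.** The point holds as a modest, optional improvement. For serial heart rate and blood pressure, the stated methods are weaker than the data allow. The firm part is lost precision: on an assumed 0.5 SD difference, about 4 to 23 points of power at 52 per group and 3.5 to 17 points at 65, depending on a baseline correlation that the protocol does not give. If that correlation is near 0.3, the gain is small. The conditional part is the false-positive risk of about 9% to 25% per vital sign, which arises only if 4 to 8 time points are each tested at 0.05. The size of both parts rests on assumed inputs.

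**What to change.** In the Statistical analysis plan section, under 2 (Statistical Analysis), state that heart rate and blood pressure over time are compared by a linear mixed model with group, time, group-by-time and the baseline value of the same variable as covariate, at time points listed in advance. Report one overall group difference per vital sign, averaged over those time points, with its 95% confidence interval. If only one time point is reported, use ANCOVA with the same baseline in place of the two-sample test. Both can be run in SPSS 22, which the protocol already names.

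Define baseline for the analysis as the last reading before study oxygen and sufentanil are started. The oxygen route differs by arm before induction, and sufentanil is given as pre-oxygenation begins, so a later pre-induction reading, above all of SpO₂, may already reflect allocation or drug effect. Reconcile the two blood pressure intervals so that the time points can be specified.

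The cost is one or two sentences on the model and one defining baseline, slightly more analysis work, and an assumption that the later value is linearly related to baseline. No extra patients are needed, and no extra measurements provided a reading is recorded before oxygen starts.
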